## 16.0 ETHICAL AND REGULATORY CONSIDERATIONS

The following must be observed to comply with Food and Drug Administration regulations for the conduct and monitoring of clinical investigations; they also represent sound research practice:

### Informed Consent and Assent

The principles of informed consent are described by Federal Regulatory Guidelines (Federal Register Vol. 46, No. 17, January 27, 1981, part 50) and the Office for Protection from Research Risks Reports: Protection of Human Subjects (Code of Federal Regulations 45 CFR 46). They must be followed to comply with FDA regulations for the conduct and monitoring of clinical investigations.

### Institutional Review

This study must be approved by an appropriate institutional review committee as defined by Federal Regulatory Guidelines (Ref. Federal Register Vol. 46, No. 17, January 27, 1981, part 56) and the Office for Protection from Research Risks Reports: Protection of Human Subjects (Code of Federal Regulations 45 CFR 46).

### Drug Accountability

An investigator is required to maintain adequate records of the disposition of investigational drugs according to procedures and requirements governing the use of investigational new drugs as described in the Code of Federal Regulations 21 CFR 312.

### Publication and Industry Contact

The agent(s) supplied by CTEP, DCTD, NCI used in this protocol is/are provided to the NCI under a Collaborative Agreement (CRADA, CTA, CSA) between the Pharmaceutical Company(ies) (hereinafter referred to as "Collaborator(s)") and the NCI Division of Cancer Treatment and Diagnosis. Therefore, the following obligations/guidelines in addition to the provisions in the "Intellectual Property Option to Collaborator" ([http://ctep.cancer.gov/industryCollaborations2/intellectual\\_property.htm](http://ctep.cancer.gov/industryCollaborations2/intellectual_property.htm)) contained within the terms of award apply to the use of the Agent in this study:

1. Agent(s) may not be used outside the scope of this protocol, nor can Agent(s) be transferred or licensed to any party not participating in the clinical study. Collaborator(s) data for Agent(s) are confidential and proprietary to Collaborator(s) and shall be maintained as such by the investigators. The protocol documents for studies utilizing Agents contain confidential information and should not be shared or distributed without the permission of the NCI. If a copy of this protocol is requested by a patient or patient's family member participating on the study, the individual should sign a confidentiality agreement. A suitable model agreement can be downloaded from: <http://ctep.cancer.gov>.

2. For a clinical protocol where there is an investigational Agent used in combination with (an)other investigational Agent(s), each the subject of different Collaborative Agreements, the access to and use of data by each Collaborator shall be as follows (data pertaining to such combination use shall hereinafter be referred to as "Multi-Party Data"):
  - a. NCI will provide all Collaborators with written notice regarding the existence and nature of any agreements governing their collaboration with NCI, the design of the proposed combination protocol, and the existence of any obligations which would tend to restrict NCI's participation in the proposed combination protocol.
  - b. Each Collaborator shall agree to permit use of the Multi-Party Data from the clinical trial by any other Collaborator solely to the extent necessary to allow said other Collaborator to develop, obtain regulatory approval or commercialize its own investigational Agent.
  - c. Any Collaborator having the right to use the Multi-Party Data from these trials must agree in writing prior to the commencement of the trials that it will use the Multi-Party Data solely for development, regulatory approval, and commercialization of its own Agent.
3. Clinical Trial Data and Results and Raw Data developed under a Collaborative Agreement will be made available exclusively to Collaborator(s), the NCI, and the FDA, as appropriate and unless additional disclosure is required by law or court order as described in the IP Option to Collaborator ([http://ctep.cancer.gov/industryCollaborations2/intellectual\\_property.htm](http://ctep.cancer.gov/industryCollaborations2/intellectual_property.htm)). Additionally, all Clinical Data and Results and Raw Data will be collected, used and disclosed consistent with all applicable federal statutes and regulations for the protection of human subjects, including, if applicable, the Standards for Privacy of Individually Identifiable Health Information set forth in 45 C.F.R. Part 164.
4. When a Collaborator wishes to initiate a data request, the request should first be sent to the NCI, who will then notify the appropriate investigators (Group Chair for Cooperative Group studies, or PI for other studies) of Collaborator's wish to contact them.
5. Any data provided to the Collaborator(s) for Phase III studies must be in accordance with the guidelines and policies of the responsible Data Monitoring Committee (DMC), if there is a DMC for this clinical trial.
6. Any manuscripts reporting the results of this clinical trial must be provided to CTEP by the Group office for Cooperative Group studies or by the principal investigator for non-Cooperative Group studies for immediate delivery to Collaborator(s) for advisory review and comment prior to submission for publication. Collaborator(s) will have 30 days from the date of receipt for review. Collaborator shall have the right to request that publication be delayed for up to an additional 30 days in order to ensure that Collaborator's confidential and proprietary data, in addition to the Collaborator(s)'s intellectual property rights, are protected. Copies of abstracts must be provided to CTEP for forwarding to Collaborator(s) for courtesy review as soon as possible and preferably at least three (3) days prior to submission, but in any case, prior to presentation at the meeting or publication in the proceedings. Press releases and other media presentations must also be forwarded to CTEP prior to release. Copies of any manuscript, abstract and/or press release/media presentation should be sent to: E-mail: [[contact]](mailto:[contact]).

The Regulatory Affairs Branch will then distribute them to the Collaborator(s). No publication, manuscript or other form of public disclosure shall contain any of the Collaborator's confidential/proprietary information.

Monitoring

This study will be monitored by the Clinical Data Update System (CDUS) Version 3.0. Cumulative CDUS data will be submitted quarterly to CTEP by electronic means. Reports are due January 31, April 30, July 31 and October 31.

Confidentiality

Please note that the information contained in this protocol is considered confidential and should not be used or shared beyond the purposes of completing protocol requirements until or unless additional permission is obtained.

## 18.1 LYRIC Criteria

Lugano Classification was developed based on treatment with cytotoxic agents. Immunotherapeutic drugs may produce antitumor effects by potentiating endogenous cancer-specific immune responses. The response patterns seen with such an approach may extend beyond the typical time course of responses seen with cytotoxic agents and can manifest as clinical responses after initial increases in tumor burden or even the appearance of new lesions.

Thus, the 2014 Lugano Classification may not provide an accurate assessment of response to immunotherapeutic agents. Provisional modification of the Lugano criteria (LYRIC Criteria) may be used to assess participants who meet progressive disease per Lugano Classification. (1,2)

The LYmphoma Response to Immunomodulatory therapy Criteria (LYRIC) has recently been proposed for tumor response assessment after immunomodulatory therapies such as immune checkpoint inhibitors. (3) These criteria address possible flare phenomenon or pseudoprogression that may be misclassified as progressive disease (PD) particularly during the first two or three weeks of treatment thus leading to underestimation of the clinical benefit of the treatment.

LYRIC criteria introduced a term “Indeterminate Response (IR)” to be able to distinguish between flare/pseudo-progression and true PD. A mandatory subsequent evaluation within 12 weeks is required to confirm or refute true progressive disease.

Complete Response	Partial Response	Progressive Disease
Same as Lugano	Same as Lugano	
As with Lugano with the following exceptions:
 
Indeterminate response (IR)
 
IR1: <math>\geq 50\%</math> increase in SPD of up to 6 measurable lesions in first 12 weeks of therapy without clinical deterioration
 
IR2: <math>< 50\%</math> increase in the overall SPD with
 

Appearance of a new lesion(s), or

<math>\geq 50\%</math> increase in PPD of a lesion or set of lesions at any time during treatment

 
IR(3): Increase in FDG uptake without a concomitant increase in lesion size or number
 
Patients with IR should continue on therapy and have repeat imaging after an additional 12 weeks (or sooner if clinically indicated).
 
Progressive disease criteria in these patients will be met if:
 
IR1: An additional increase in the target SPD of <math>\geq 10\%</math> between the first IR1 timepoint and the SPD being assessed; or an increase in <math>\geq 5\text{mm}</math> in either dimension of at least one lesion for lesions <math>\leq 2\text{cm}</math> and <math>10\text{mm}</math> for lesions <math>> 2\text{cm}</math>.
 
IR2: the new or growing lesion(s) should be added to the target lesions (total of no more than 6) and there is PD if the SPD if the newly defined set of target lesions has increased <math>\geq 50\%</math> from their nadir value (which may precede the IR time point).
 
IR3: There is evidence of PD by an increase in lesion size or the development of new lesions.

Abbreviations: SPD, sum of the product of the diameters; PPD, product of the perpendicular diameters.		

References

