**In the event of indeterminate PET-CT results at the end of treatment (see LYRIC criteria, Section 18.1),** the patient should be observed without additional treatment and repeat imaging should be performed after an additional 12 weeks (or sooner if clinically indicated) to determine whether there is true progressive disease. Biopsy confirmation should be sought (if safe/feasible) prior to initiation of second line therapy if repeat imaging is concerning for relapsed or refractory HL.

Please see also [Section 9.1](#) for required laboratory assessments to be performed at the EOT visit. Peripheral blood must be submitted, with patient's consent, as indicated in [Section 15.2](#).

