7.8 Criteria for Removal from Protocol Treatment

- a. Completion of protocol treatment (either completion of 6 cycles of study drug or (where applicable) completion of radiation therapy, whichever is later).
- b. Progression of disease or symptomatic deterioration (as defined in [Section 10.1](#)).
- c. Unacceptable toxicity per treating physician or study chair recommendation.
- d. Treatment delay of all components of study regimen (BV or nivolumab AND AVD) for any reason > 28 days.
- e. Unplanned radiation therapy (that was not declared as intent-to-treat with Residual PET RT at date of registration and/or does not meet criteria in [Section 7.5](#)).
- f. The patient may withdraw from the protocol treatment at any time for any reason.

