## 10.0 CRITERIA FOR EVALUATION AND ENDPOINT ANALYSIS

Response and progression will be evaluated in this study using the revised international working group guidelines (Lugano classification) (101).

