#### b. Metabolic Response at the end of Cycle 6 or end of treatment.

##### 1. Complete Metabolic Response (CR) (as defined by all the following):

- a. Deauville Score of 1, 2, or 3 with or without a residual mass or nodal lesion:
  - 1, no FDG uptake above background;
  - 2, FDG uptake  $\leq$  mediastinum;
  - 3, FDG uptake  $>$  mediastinum but  $\leq$  liver.
- b. In Waldeyer's ring or extranodal sites with high physiologic uptake or with activation within spleen or marrow (e.g., with chemotherapy or myeloid colony-stimulating factors), uptake may be greater than normal mediastinum and/or liver. In this circumstance, complete metabolic response may be inferred if uptake at sites of initial involvement is no greater than surrounding normal tissue even if the tissue has high physiologic uptake.
- c. No new lesions.
- d. No evidence of FDG avid disease in marrow unless as noted in [Section 10.1b.1b](#).
- e. In the event that a bone marrow biopsy is performed at baseline and the patient had evidence of marrow involvement by bone marrow biopsy at baseline, a repeat marrow will be required to confirm CR. A sample that is negative by immunohistochemistry but that demonstrates a small population of clonal lymphocytes by flow cytometry will be considered a CR.

2. Partial Metabolic Response (PR) (as defined by all the following):
  - a. Deauville Score of 4 or 5 with reduced uptake compared to baseline and residual mass(es) of any size.
  - b. No new lesions.
  - c. In the event that a bone marrow biopsy is performed at baseline: Residual marrow uptake higher than uptake in normal marrow but reduced compared with baseline (diffuse uptake compatible with reactive changes from chemotherapy allowed). If there are persistent focal changes in the marrow in the context of a nodal response, consideration should be given to further evaluation with a BM biopsy.
3. No Metabolic Response (SD) (as defined by all the following):
  - a. Deauville Score 4 or 5 with no significant change in FDG uptake from baseline at interim or end of treatment.
  - b. No new lesions.
  - c. No change in marrow uptake from baseline.
4. Progressive Metabolic Disease (PD) (as defined by any of the following):
  - a. Deauville Score 4 or 5 with an increase in intensity of uptake from baseline.
  - b. New FDG-avid foci consistent with lymphoma.
  - c. New or recurrent FDG-avid foci in the bone marrow.

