#### 10.4 **Progression Free Survival (PFS)**

From date of registration to date of first observation of progressive disease according to the 2014 Lugano classification, or death due to any cause. Patients last known to be alive and without report of progression are censored at date of last contact. See [Sections 10.1b.4](#) and [18.7](#) for definition of progressive disease according to 2014 Lugano classification.

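### Appendix 18.1 lets LYRIC reassess patients who already meet Lugano progression, and no sentence says which classification is reported for PFS

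*Combined protocol and SAP*

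**What the plan says.** The endpoint text is Lugano only. Section 10.0: "Response and progression will be evaluated in this study using the revised international working group guidelines (Lugano classification". Section 10.4 defines PFS as "From date of registration to date of first observation of progressive disease according to the 2014 Lugano classification, or death due to any cause", with no confirmation step and with references to Sections 10.1b.4 and 18.7. Sections 10 and 11 do not mention LYRIC. Section 2.1 lists outcomes under LYRIC as something to be studied in addition to the primary objective.

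Appendix 18.1 says that LYRIC "may be used to assess participants who meet progressive disease per Lugano Classification". It sets no limit by arm or by purpose and does not mention PFS. Its table presents indeterminate response as a set of exceptions to Lugano progression and adds: "Patients with IR should continue on therapy and have repeat imaging after an additional 12 weeks (or sooner if clinically indicated".

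Section 7.4c, for indeterminate end-of-treatment results, refers to Appendix 18.1. It asks for observation without further treatment and says that "repeat imaging should be performed after an additional 12 weeks (or sooner if clinically indicated) to determine whether there is true progressive disease". Section 7.5 has similar text for patients declared for radiotherapy. Section 7.8 lists "Progression of disease or symptomatic deterioration", as defined in Section 10.1, as a reason to leave protocol treatment.

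**The concern.** The patients whom Appendix 18.1 allows to be reassessed are exactly those who, under Section 10.4, have already had a PFS event. A site that follows Section 7.4c and the appendix could reasonably conclude that the first scan is not yet progression, and so not report it.

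The trial is open label (Section 7.1a) and responses are read locally (Section 7.4). The purposes of central review in Section 12.2 are stage, Cycle 2 response, end-of-treatment response and radiotherapy eligibility; the date of progression is not among them. The 12-week repeat scan is not a listed image-submission time point in Section 15.4a. The only PFS sensitivity analysis in Section 11.1 concerns non-protocol therapy. If LYRIC led to under-reporting in one arm, no planned analysis is aimed at showing it.

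Use is more likely in Arm 1. The rationale in Appendix 18.1 is immunotherapy, Section 7.4c warns of false-positive scans in Arm 1, and the radiotherapy monitoring text in Section 11.2 refers to possible false progressions with N-AVD. Uncounted events in Arm 1 alone would favour N-AVD on the primary endpoint.

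**Working it through.** **The same scan under two rules**

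| Finding | Sections 10.1b.4 and 18.7 | Appendix 18.1 |
|---|---|---|
| "Deauville Score 4 or 5 with an increase in intensity of uptake from baseline", lesions unchanged in size and number | Progression | IR3: "Increase in FDG uptake without a concomitant increase in lesion size or number" |
| New FDG-avid foci consistent with lymphoma | Progression | Can be IR2, if the overall sum of products rises by less than 50% |

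No sentence says which column goes on the form.

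**The plan's own figures (Section 11.1)**

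Inputs: 470 eligible patients per arm, uniform entry over 4 years, 2 further years of follow-up. Control PFS is 0.70 + 0.30·exp(−0.38t). Experimental PFS is 0.74 + 0.26·exp(−0.38t/1.67).

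Expected events per arm = 470 × p × [1 − (exp(−2λ) − exp(−6λ))/(4λ)], where p is the fraction not cured.
- Control (p = 0.30, λ = 0.38): 107.1
- Experimental (p = 0.26, λ = 0.38/1.67): 71.3
- Total: 178.4, against the stated 179

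The overall one-sided alpha from 0.005, 0.005 and 0.021 at information 0.5, 0.75 and 1 is 0.0241, consistent with the stated limit of 0.025. The design reproduces.

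**Events never counted, Arm 1 only: approximation**

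Under the null there are 179/2 = 89.5 events per arm. If k Arm 1 events are never counted:

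shift = ln[89.5/(89.5 − k)] × √[(179 − k)/4]; error = 1 − Φ(2.034 − shift)

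| k | shift | one-sided error |
|---|---|---|
| 0 | 0 | 0.021 |
| 3 | 0.0341 × 6.633 = 0.226 | 0.035 |
| 5 | 0.0575 × 6.595 = 0.379 | 0.049 |
| 8 | 0.0936 × 6.538 = 0.612 | 0.078 |

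**Delay and loss separated: simulation**

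940 patients, cut at 179 counted events, unstratified log-rank at 0.021, no interim stopping; 8,000 runs under the null and 4,000 under the alternative. Early events are those in the first 32 weeks (24 weeks of treatment plus up to 8 weeks to the end-of-treatment scan). Under the null this is 470 × 0.30 × [1 − exp(−0.38 × 32/52)] = 29.4 per arm. The share lost is an assumption; the documents give none.

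| Scenario under the null | Hazard ratio, control vs experimental | one-sided error |
|---|---|---|
| Strict Section 10.4 | 1.00 | 0.019 |
| All early Arm 1 events delayed 12 weeks | 1.01 | 0.024 |
| 10% of early Arm 1 events lost (about 3) | 1.04 | 0.037 |
| 20% lost (about 6) | 1.08 | 0.064 |
| 30% lost (about 9) | 1.12 | 0.107 |
| 50% lost (about 15) | 1.22 | 0.235 |
| 30% lost in both arms | 1.00 | 0.022 |

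Power under the alternative is 84% both with strict dating and with the 12-week delay. Monte Carlo error on the type I error is about 0.002 to 0.005.

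**The case against.** The strongest reply is that Section 10.4 governs. Sections 10.0, 10.4, 7.4 and 18.13 all name Lugano, Section 10.4 fixes the event at the first such observation, and Appendix 18.1 is only permissive. That stands: applied as written, Section 10.4 neither delays nor erases an event. A reader might infer that the plan holds two competing definitions of PFS. The documents do not support that, because the appendix never mentions PFS.

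It can also be said that the protocol separates formal progression from management. Sections 7.4b and 10.5 use the term formal progression, and the 12-week text in Section 7.4c concerns observation, imaging and biopsy before second-line therapy. Section 7.5 speaks of residual avid lesions, which with reduced uptake and no new lesions are a Lugano partial response and not a PFS event. This is a fair reading, but it is not stated. LYRIC's indeterminate category, to which Section 7.4c refers, exists only as an exception to progression.

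Assessment forms, reports and images are collected at the main time points (Sections 14.4 and 15.4), and CT is required at 1 and 2 years (Section 7.6). Much true progression would therefore surface later, and many Lugano events could be identified retrospectively. This makes a lost event less likely. It does not tell a site what to report, and the documents do not say that central review overrides the local read.

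**Conclusion.** The point holds as an unreconciled ambiguity about which classification is reported for the primary endpoint. Two stated rules can classify the same scan differently, and local readers who know the treatment arm are pointed to both.

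The size depends on what sites do. A pure 12-week delay is close to harmless (error 0.024 against a simulated 0.019, power unchanged). Loss confined to Arm 1 is not: about 3 uncounted events take the final test to roughly 0.035, above the trial's overall limit of 0.025, and 5 or 8 take it to 0.049 or 0.078. These figures are hypothetical. They assume that the events are never counted later and that the loss occurs in one arm only. Loss of 30% of early events in both arms leaves the error at 0.022.

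A reader might go further and infer that the plan will bias the comparison towards N-AVD. The documents do not support that: they give no reclassification rate, Appendix 18.1 and Section 7.4c apply to both arms, and heavier use in Arm 1 is a reasonable inference only.

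**What to change.** State in Sections 10.4 and 7.4c and in Appendix 18.1 that, whatever LYRIC category is assigned, the first Lugano progression is recorded and dated for PFS, and for the progression component of EFS (Section 10.5), in both arms. Record the LYRIC category and date in parallel in both arms. Report LYRIC-based PFS as a labelled sensitivity analysis; Section 2.1 already foresees outcomes under LYRIC.

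This is a cheap improvement. It costs one sentence in three places, one extra recorded category and date, and one extra analysis run. Sample size, alpha and the PFS definition do not change.

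Separately, the sponsor should reconcile the management passages. For patients with an indeterminate finding, Appendix 18.1 says to continue therapy, Section 7.4c says to observe without further treatment at end of treatment, and Section 7.8 removes patients at progression as defined in Section 10.1. Within Appendix 18.1, the text sets re-evaluation within 12 weeks and the table after a further 12 weeks. Which rule is right is a clinical matter on which this point takes no position.

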18.2 Quality of Life

a. Quality of Life Objectives

To compare between arms patient-reported fatigue, neuropathy and health-related quality of life over time (baseline prior to registration, at Day 56 (corresponding to the beginning of Cycle 3), 4-8 weeks after the last dose of protocol therapy (following last dose of study drug or radiation therapy, whichever is later), and 1 and 3 years after randomization) using the PROMIS-Fatigue (or Ped PROMIS Fatigue), the FACT/GOG-Ntx, and the PROMIS Global (or Ped PROMIS-Global), respectively

1. Hypothesis: 1: Patients randomly assigned to the N-AVD arm will have worse fatigue scores during initial treatment with resolution by one-year post treatment than patients randomly assigned to the BV arm. Patients receiving both nivolumab and radiation therapy will have worse fatigue than recipients of nivolumab without radiation. Self-reported fatigue and HRQL will be measured by the PROMIS Fatigue scale(s) (adult or pediatric versions) and PROMIS-Global or Pediatric PROMIS-Global, respectively.
2. Hypothesis 2: Patients randomly assigned to the BV-AVD will have worse FACT/GOG-Ntx scores on treatment and by 1 year after the completion of treatment, as compared to patients randomly assigned to the N-AVD arm. Scores will be worse for patients 40 years or older.

b. Background

Patients with newly diagnosed, advanced stage HL are at risk for poor HQRL as a result of their underlying disease and its treatment -- whether dose-dense chemotherapy alone or in combination with planned radiotherapy. Several studies in adults with HL have also demonstrated that a subset of patients report severe fatigue at the time of diagnosis (est. 10%) and that for some fatigue persists long after completion of therapy. The introduction of novel therapies into the upfront treatment of HL, including the antibody-drug conjugate Brentuximab vedotin (BV) and PD-1 inhibitors, such as Nivolumab offer the promise of improved disease-free and overall survival, the potential reduction of radiotherapy, and the associated decrease in late effects. These agents, however, are associated with their own symptoms burden, such as peripheral neuropathy (BV) or rashes, colitis, pneumonitis, and endocrinopathies (Nivo). Recent studies suggest a rate of peripheral sensory neuropathy of 20% or higher with BV, and toxicity that was associated with premature abandonment of the experimental arm on the ECHELON1 trial. The long term impact of Nivo on HRQL after successful immunomodulation of the tumor is not known, although recent studies have demonstrated the relationship between adverse events and poorer HRQL. Hence, we propose the first study to capture longitudinal HRQL, anchored to symptom burden in pediatric and adult patients with advanced stage HL.

Recently validated measures within the constructs of overall HRQL, fatigue, and patient-reported symptoms afford us with an instrument battery that is targeted and brief, spans the full age span of the trial population, and generally available in the needed target languages (i.e., English, Spanish, and French).

In the current Children's Oncology Group (COG) Phase III trial in HL (AHOD 1331; NCT02166463) in which we are evaluating the inclusion of BV into the existing chemotherapy backbone, we have serially measured HRQL, patient-reported CIPN, health care utilization and health utilities from more than 300 children and where appropriate, from their parent proxies. (Proxy report was used in children under 11 years, who could not provide unassisted self-report). We have collected provider grading of targeted toxicities, most notably peripheral neuropathy, at each cycle. More than 97% of eligible patients participated in the study, completing baseline measures prior to the start of planned therapy. At scheduled follow up time points (Cycle 2, D8; Cycle 5, D8; 6-8 weeks off therapy; 12- and 36- months off-therapy), we have collected measures from 95% of participants. Similar to the proposed study, we have begun the analysis with aggregate results (preserving the blinding by study arm) with the plan of ultimately comparing by study arm, following completion of full trial accrual.

c. Quality of Life Instruments

In this study we rely on validated measures (PROMIS Global, PROMIS fatigue, and FACT/GOG-Ntx) to be completed by patients in a 15-minute period at key clinical time points during the trial. All of these instruments are available and have been validated for both youth and adult self-report in English, French, and Spanish, allowing for broad participation across the age span of the trial population. Moreover, the youth and adult versions of the same instruments have been determined to measure the same constructs, enabling us to combine the age groups into unified analyses, stratified by age.

1. PROMIS Fatigue

